Appendix A Visual Analog Scale

1. Background

Corticosteroid therapy, including intralesional and topical applications, has many indications within the fields of Dermatology, Plastic Surgery, and Orthopedics. However, these injections can be quite painful, which leads many patients to discontinue treatment.

Often, the injection involves a mixture of local anesthetic and corticosteroids despite a lack of evidence that the use of lidocaine improves pain.^{1,2} Due to the acidic pH, the lidocaine component of the injection can actually cause a significant burning sensation during the procedure. Lidocaine does not have anti-inflammatory properties and does not treat the underlying pathology. By including another medication, lidocaine also adds cost and risk to the procedure.

In a double blind, randomized control trial, Osanakornkul and Burusapat studied the benefit of applying topical anesthetics or a 1:1 mixture of 1% lidocaine and triamcinolone acetonide at the injection site to alleviate pain during keloid treatment.² While the use of a topical anesthetic 1 hour prior to the injection was able to alleviate the pain from needle stick, the study did not show a statistical difference in pain outcomes with the use of lidocaine. However, this study was limited to the use of intralesional corticosteroid injections for the treatment of keloids. In addition, the study only focused on 3 locations: the shoulder, sternum, and ear. Keloid injections are often more painful than other injections because the horizontal penetration of the needle can pierce a large number of nerve endings. In routine injections, the entry of the needle is either vertical or angled and thus pierces a small number of nerve endings.³ In addition, the injected material stretches nerve endings and compresses them against unyielding keloid tissue, causing substantial pain that can persist up to several hours after the procedure.³ This study will examine intralesional corticosteroid injections for keloids, alopecia areata, and other indications while including a wider variety of injection sites.

2. Rationale and Specific Aims

The purpose of this study is to see if removing lidocaine from intralesional injections decreases pain of the injection. We hypothesize there will be no difference in pain outcomes if lidocaine is removed from intralesional corticosteroid injections.

3. Animal Studies and Previous Human Studies

A similar study was conducted in plastic surgery with intraarticular injections for trigger finger. The project examined pain outcomes for injections containing steroid + normal saline vs steroid + local anesthetic. The results indicated that injections containing local anesthetic were significantly more painful. Thus, including a mixed local anesthetic in the injection adds unnecessary cost and risk to the procedure. Because steroid injections in dermatology are also commonly mixed with a local anesthetic, this study design can be applied to these intralesional injections as well.

4. Inclusion/Exclusion Criteria

Inclusion Criteria:

- >12 years old presenting with an indication for intralesional steroid injection

Exclusion Criteria:

- Not a candidate for corticosteroid injection
- Contraindication to lidocaine

5. Enrollment/Randomization

All patients meeting inclusion/exclusion criteria will be offered enrollment. Using a coin flip, patients will have a 50% chance of receiving one of the following treatments:

1. Corticosteroid + lidocaine
2. Corticosteroid + normal saline

6. Study Procedures

Day 1 (In clinic): After diagnosing the need for an intralesional injection, patients will be screened for enrollment. The consent form will be reviewed in depth to describe the purpose and procedures associated with the study. If they agree to be part of the study, we will collect the following demographic information:

- MRN
- Age
- Gender
- Comorbidities (chronic opioid use, smoking, diabetes, neuropathy, fibromyalgia)
- Phone number
- Site of injection (scalp, face, neck, and trunk)
- Indication for injection

The patient will then be randomized to receive one of the following injections:

1. Corticosteroid with normal saline
2. Corticosteroid with lidocaine

A co-investigator will prepare the syringe to ensure blinding. The injection site will be prepped in sterile fashion with an alcohol wipe. The physician will then administer the injection. Immediately following the injection, the patient will be asked to rate the pain of the injection based on the visual analog scale (appendix A). Specifically, the co-investigator will say "Rate the injection experience on a scale of 0 to 10, 0 being no pain and 10 being the worst pain of your life". A bandaid will be placed over the injection site and the patient will be reminded to expect a phone call that afternoon and the next day.

Day 1 (after clinic): Approximately 6 hours after the injection, a different study investigator will call the patient by phone to assess their current pain level with the visual analog scale. Using a different investigator who is unaware of the treatment arm for follow-up will further ensure blinding. Specifically, the investigator will say "Rate your

current pain level from the injection on a scale of 0 to 10, 0 being no pain and 10 being the worst pain of your life". Patients will be called up to three times before being considered lost to follow-up.

Day 2: Approximately 24 hours after the injection, the study investigator will again call the patient by phone to assess their current pain level with the visual analog scale. Specifically, the investigator will say "Rate your current pain level from the injection on a scale of 0 to 10, 0 being no pain and 10 being the worst pain of your life". Patients will then be thanked for their involvement in the study and encouraged to reach out to the principle investigator or clinic should any problems arise. Patients will be called up to three times before being considered lost to follow-up.

7. Risks

This study is categorized as less than minimal risk. We are comparing two treatment methods that are accepted as standard of care, and are already used on the clinic population being studied on a daily basis. There is no new experimental intervention that would put patients at greater than minimal risk. Although rare, the risks of a corticosteroid injection include hypopigmentation, skin atrophy, and hyperglycemia in patients with diabetes. There is also a small risk of an allergic reaction to the lidocaine component. There may be unknown or unanticipated adverse effects.

8. Reporting of Adverse Events or Unanticipated Problems Involving Risk to Participants or Others

Adverse events will be reported to the IRB immediately through standard reporting mechanisms.

9. Study Withdrawal/Discontinuation

There are no anticipated circumstances under which subjects would be withdrawn from research without their consent. If subjects withdraw, there will be no penalty or consequences.

10. Statistical Plan

We are planning a study of a continuous response variable from independent control and experimental subjects with 1.1538 control(s) per experimental subject. In a previous study the response within each subject group was normally distributed with standard deviation 0.3. If the true difference in the experimental and control means is 0.2, we will need to study 34 experimental subjects and 39 control subjects to be able to reject the null hypothesis that the population means of the experimental and control groups are equal with probability (power) 0.8. The Type I error probability associated with this test of this null hypothesis is 0.05.

11. Privacy/Confidentiality Issues

Private health information (PHI) will be used in the study, but not disclosed. All PHI will be stored on a secure, password-locked server. All participants in the study have obtained Human Research certification to have the necessary authorization to PHI. When collecting patient data, only medical record numbers will be used to identify patients.

[figure not shown]
12. Follow-up and Record Retention

The study will last for approximately 1 year after initiation or until the enrollment goal is met. At the study conclusion, all identifiable data will be destroyed and de-identified data will be kept for analysis.

13. References:

2. Usanakornkul, A., & Burusapat, C. (2017). A Topical Anesthetic and Lidocaine Mixture for Pain Relief During Keloid Treatment. *Dermatologic Surgery*, 43(1), 66-73. doi:10.1097/dss.0000000000000932
3. Mishra S Safe and less painful injection of triamcinolone acetonide into a keloid—a technique. *J Plast Reconstr Aesthet Surg* 63:e205

Appendices:

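### Section 2 hypothesises no difference in pain, but the only test planned in Section 10 can reject that hypothesis and cannot support it

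*Combined protocol and SAP*

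**What the plan says.** Section 2 puts two statements side by side. The purpose is directional: "The purpose of this study is to see if removing lidocaine from intralesional injections decreases pain of the injection". The hypothesis that follows is not: "We hypothesize there will be no difference in pain outcomes if lidocaine is removed from intralesional corticosteroid injections".

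Section 10 is the whole statistical plan, and it is a single sample-size paragraph. It gives the planning difference and the numbers, "If the true difference in the experimental and control means is 0.2, we will need to study 34 experimental subjects and 39 control subjects", and the aim of the test, "reject the null hypothesis that the population means of the experimental and control groups are equal with probability (power) 0.8". It adds: "The Type I error probability associated with this test of this null hypothesis is 0.05". It does not say whether the test is one- or two-sided.

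No section gives an equivalence or non-inferiority margin, a confidence-interval criterion, or a rule for reading a non-significant result. The 0.2 appears only as a true difference to be detected. Pain is rated three times (Section 6): straight after the injection, at about 6 hours and at about 24 hours. Section 10 does not say which rating is tested.

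**The concern.** A test of equal means has two outcomes. It rejects equality, which contradicts the Section 2 hypothesis, or it fails to reject, which is compatible with that hypothesis but does not establish it. If the hypothesis is what the investigators expect to report, the only result that agrees with it is p > 0.05, and that result can arise from true equality or from too little information.

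The reading matters here because of the rationale. Section 1 says of lidocaine: "By including another medication, lidocaine also adds cost and risk to the procedure". A finding taken as equal pain would then count as an argument for leaving it out. Section 1 also summarises the earlier keloid trial by saying that "the study did not show a statistical difference in pain outcomes with the use of lidocaine", so the same form of summary is easily foreseen for this trial. A non-significant result could be reported as confirming the hypothesis while the data still allow a difference as large as the planning value. That difference could be more pain without lidocaine, or the very reduction that the purpose sentence asks about.

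**Working it through.** **Inputs, all from Section 10:** 34 experimental and 39 control subjects; SD 0.3 in each group; planning difference 0.2; type I error 0.05; power 0.8.

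**Step 1: reproduce the plan's figure.**
- SE = 0.3 × √(1/34 + 1/39) = 0.0704, with df = 34 + 39 − 2 = 71.
- Noncentrality at 0.2 = 0.2/0.0704 = 2.84.
- Power from the noncentral t distribution: 0.800 two-sided at 0.05, 0.879 one-sided at 0.05.

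The two-sided test matches the stated 0.8 and the one-sided test does not. The arithmetic of Section 10 is sound, and the trial is sized as an ordinary two-sided difference trial.

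**Step 2: how often is p > 0.05?** With the critical value t(0.975, 71) = 1.994, P(p > 0.05) = P(|T| < 1.994), where T is noncentral t with noncentrality (true difference)/0.0704. Negative differences give the same values.

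| True difference | Noncentrality | P(p > 0.05) |
|---|---|---|
| 0 | 0 | 95% |
| 0.1 | 1.42 | 71% |
| 0.15 | 2.13 | 44% |
| 0.2 | 2.84 | 20% |

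**Step 3: what does the 95% CI say when p > 0.05?** The half-width at an observed SD of 0.3 is 1.994 × 0.0704 = 0.140. An observed difference is non-significant below 0.140, and its CI reaches 0.2 once it exceeds 0.2 − 0.140 = 0.060. So any observed difference between about 0.06 and 0.14 is non-significant and yet has a CI that includes 0.2. Allowing for variation in the sample SD (numerical integration, confirmed with 1,000,000 simulated trials per row):

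| True difference | CI reaches 0.2 in either direction, among trials with p > 0.05 | Whole CI within ±0.2, all trials |
|---|---|---|
| 0 | 37% | 60% |
| 0.1 | 61% | 28% |
| 0.15 | 77% | 10% |

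On these inputs the trial can be informative about similarity. The interval shows when it is; p > 0.05 does not.

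**Step 4: dependence on the SD.** At an assumed SD of 1 (not in the documents) the half-width would be about 0.47, and p > 0.05 would say less still.

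**The case against.** The strongest reply is that the hypothesis sentence is just a null hypothesis, loosely worded. Much in the documents favours that. The purpose sentence asks about a decrease in pain. Section 1 says that acidic lidocaine can itself burn. Section 3 describes a trigger-finger study that found injections with anesthetic significantly more painful, and says its design carries over to this trial. On that reading Sections 2 and 10 agree, and the fault is one of wording. This carries weight: it is why the fix below treats the trial as a difference trial. It does not clear the point, because the sentence as written is a prediction that the planned test cannot support, and nothing elsewhere says how a non-significant result is to be read.

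A second reply is that the harm is inferred. That is right as far as it goes. A reader might infer that the investigators intend to present p > 0.05 as proof of equal pain, but the documents do not say so. What stands is a foreseeable risk.

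A third is that 0.2 is never called clinically important. This also stands. A reader might take 0.2 as the margin for similarity, but Section 10 offers it only as a planning value. The Step 3 figures show what the interval would leave open at that value, not that a difference of 0.2 matters to patients. The 37% at a true difference of 0 also counts both directions; for one named direction it is 18%.

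Finally, every percentage in Steps 2 and 3 rests on SD 0.3. A larger SD would make the interpretive risk greater, not smaller.

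**Conclusion.** The point holds, and should be fixed. The stated hypothesis and the only planned test do not match: the test can reject no difference but cannot support it. On the plan's own inputs, p > 0.05 is expected in 95% of trials at a true difference of 0, in 71% at 0.1, in 44% at 0.15 and in 20% at 0.2, so it must not be read as confirming the hypothesis.

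This rests on a two-sided t-test with 34 and 39 analysed patients and SD 0.3. Sidedness is inferred from the match to 80% power. Confidence is medium, because the intent behind the hypothesis sentence is uncertain.

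A reader might go further and conclude that the test is invalid, that the sample size is miscalculated, or that the trial can say nothing about similarity. The documents support none of these. The test fits the purpose sentence, 34 and 39 reproduce, and on these inputs the 95% CI would lie wholly within ±0.2 in 60% of trials if the true difference were 0.

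**What to change.** Make these changes before data are seen.

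- **Section 2.** Reword the hypothesis to match the planned test, for example: *We test, two-sided, whether mean pain rated immediately after injection differs when lidocaine is removed.* If the investigators regard another time point as the main one, name that instead.
- **Section 10.** Add: *The mean difference (saline minus lidocaine) at that time point will be reported with its 95% CI. A p-value above 0.05 alone will not be reported as showing no difference.*

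This applies if the trial is a difference trial. The cost is a few sentences and one reported interval, with the sample size unchanged. What is given up is that a non-significant result can no longer be claimed as confirming the hypothesis.

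If the investigators truly aim to show no difference, or that saline is not worse, rewording is not enough. They must pre-specify and justify a margin and restate the power at 34/39 for it, and more patients may be needed. The documents give no margin. For illustration only, with SD 0.3, a true difference of 0 and assumed margins of 0.15, 0.2 and 0.25, the power at 34/39 to show equivalence is 36%, 76% and 94% with a 90% CI, or 13%, 60% and 88% with a 95% CI.

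### No pain rating is taken before the injection and no covariate adjustment is planned, so any carry-over of pre-existing pain into the ratings cannot be directly checked or adjusted for

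*Combined protocol and SAP*

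**What the plan says.** **Who enters.** Section 4 has one inclusion criterion, ">12 years old presenting with an indication for intralesional steroid injection", and two exclusions, "Not a candidate for corticosteroid injection" and "Contraindication to lidocaine". None concerns pain. Section 1 makes the breadth deliberate: "This study will examine intralesional corticosteroid injections for keloids, alopecia areata, and other indications while including a wider variety of injection sites".

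**What is recorded before randomisation.** Section 6 lists seven items: record number, age, gender, comorbidities, phone number, injection site and indication. The comorbidity item reads "Comorbidities (chronic opioid use, smoking, diabetes, neuropathy, fibromyalgia". No pain score is on the list.

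**When pain is rated.** Section 6 places the first rating after treatment: "Immediately following the injection, the patient will be asked to rate the pain of the injection based on the visual analog scale". The spoken question is "Rate the injection experience on a scale of 0 to 10, 0 being no pain and 10 being the worst pain of your life". At about 6 and 24 hours the caller asks for the "current pain level from the injection on a scale of 0 to 10, 0 being no pain and 10 being the worst pain of your" (final word omitted).

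**What is analysed.** Section 10 is a sample-size statement for a comparison of two independent means. It names no covariate, stratification factor or subgroup. Section 5 allocates by an unstratified coin flip.

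**The concern.** The outcome is a self-reported pain score in a population chosen to be broad. The investigators evidently regard some conditions that can alter pain as worth recording, but they do not measure pain itself before they cause some.

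At the immediate rating the patient has just felt the needle and the question is about that event. At 6 and 24 hours the task is harder: the patient must say how much of the pain felt now comes from the injection rather than from the lesion or another condition. Injection pain may also be small by 24 hours. If part of the background pain enters the answer, it adds variance. If the arms happen to differ in background pain, the estimated difference shifts, and nobody could see this directly in the data.

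The hypothesis in Section 2 is that pain will not differ between arms. Unexplained variance makes a non-significant result more likely, and such a result could be misread as support for that hypothesis. A baseline rating also cannot be recovered once the injection has been given.

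**Working it through.** **1. Section 10's own figure.** Inputs: difference 0.2, SD 0.3, 34 experimental and 39 control patients, type I error 0.05 (sidedness not stated; two-sided reproduces the figure).

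- Standardised difference: 0.2 / 0.3 = 0.667.
- Standard-error factor: sqrt(1/34 + 1/39) = 0.2346.
- Noncentrality: 0.2 / (0.3 × 0.2346) = 2.84, on 34 + 39 − 2 = 71 degrees of freedom.
- Two-sided t-test power: 80.0%.

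The stated sample size reproduces, so the point does not rest on an arithmetic error.

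**2. What a baseline covariate could gain.** If the rating before injection has correlation r with the rating after it, adjustment leaves a residual variance of (1 − r²) times the original, so the SD becomes 0.3 × sqrt(1 − r²). The documents give no r; the range below is an assumption.

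| r (assumed) | 1 − r² | Residual SD | Noncentrality | Power, 34 vs 39 |
|---|---|---|---|---|
| 0 | 1.00 | 0.300 | 2.84 | 80.0% |
| 0.1 | 0.99 | 0.298 | 2.86 | 80.4% |
| 0.2 | 0.96 | 0.294 | 2.90 | 81.6% |
| 0.3 | 0.91 | 0.286 | 2.98 | 83.6% |
| 0.5 | 0.75 | 0.260 | 3.28 | 89.9% |

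The covariate uses one degree of freedom (70 instead of 71). At r = 0 power is still 80.0%, so a useless covariate costs almost nothing. If nearly all patients report 0 before injection, the result is close to the first row.

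**3. What unmeasured leakage could cost.** This is an illustration only. Suppose pre-existing pain enters the rating in full, as independent variance on top of the planned SD of 0.3. The documents give no SD for such pain; 0.1 to 0.3 points on the 0-10 scale is assumed. Total SD is sqrt(0.3² + s²), and the SD of the chance difference between arms is s × 0.2346.

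| s (assumed) | Total SD | t-test power | SD of chance imbalance |
|---|---|---|---|
| 0.1 | 0.316 | 75.8% | 0.02 |
| 0.2 | 0.361 | 64.5% | 0.05 |
| 0.3 | 0.424 | 50.9% | 0.07 |

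The last column is to be read against the target difference of 0.2. The table shows that the design has almost no slack if background pain adds to the planned SD. It does not show that background pain does so.

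**The case against.** **The questions already separate the two.** All three ratings are directed at the injection, and the first asks about an event that has just happened. This stands. A reader might infer that injection pain cannot be separated from pain already present; the documents do not support that, because the protocol separates them by the patient's own attribution. What remains is that the attribution cannot be checked without a baseline, and that it is least secure at 6 and 24 hours.

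**Randomisation deals with it.** In expectation, yes. A reader might infer a biased treatment comparison; that would be wrong. Only added variance and chance imbalance remain, and these apply to any unmeasured prognostic factor. They deserve attention here because this factor is so cheap to measure.

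**Data already collected can help.** Comorbidities, site and indication are recorded before randomisation, so their balance can be inspected and they could serve as covariates. It would be too strong to say that nothing in the data can correct for background pain. But they are partial proxies: a diagnosis does not measure pain at the lesion that day, and no analysis use is stated for any of them.

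**The lesions may not hurt.** No section says that they are painful before treatment, or that patients with the listed conditions confuse the two kinds of pain. This stands, and is why the gain may be nil.

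**The planned SD may already contain background variation.** It is a within-group SD from a previous study. The documents therefore do not show that the trial is underpowered on this account, and the second table must not be read that way.

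**A question about the lesion misses widespread pain.** Also true: it would not capture fibromyalgia or neuropathic pain elsewhere. It addresses the site where confusion with injection pain is most likely.

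**Conclusion.** The concern holds as a missed, inexpensive gain in precision and in the ability to check the ratings, not as a flaw that invalidates the comparison. Established from the documents: eligibility is open to any indication and to patients with pain-modifying conditions, no rating precedes the injection, and no adjustment is planned.

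The size is uncertain. On Section 10's inputs the gain in power runs from about 0 to 10 percentage points (80.0% to 89.9%) over assumed correlations of 0 to 0.5, with the low end applying if most patients have no pain beforehand. These figures take the planned difference and SD at face value and treat the same inputs as applying at each time point, since Section 10 does not say which rating they describe.

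**What to change.** - **Section 6:** add an eighth item to the data collected after consent and before the coin flip, namely current pain at the lesion on the same 0-10 scale with the same anchors.
- **Section 10:** prespecify that value as a covariate in the between-arm comparison at all three time points (analysis of covariance), and report its distribution by arm.
- **Section 4:** no change, so the broad population is kept.

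The cost is one spoken question per patient in a visit that already collects seven items, and one model degree of freedom. No additional visit, procedure or patient is needed. The question has to be in place before a patient is injected, so the change is best made before enrolment starts.

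### Section 5 allocates by an unrestricted coin flip, with no described sequence, concealment or log to check it against and no balancing or adjustment for keloid versus other indications

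*Combined protocol and SAP*

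**What the plan says.** Section 5 (Enrollment/Randomization) states: "Using a coin flip, patients will have a 50% chance of receiving one of the following treatments". The two arms follow, and nothing more is said about method.

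Section 6 (Study Procedures) sets the order. The patient consents, then age, gender, comorbidities, injection site and indication are collected, and then: "The patient will then be randomized to receive one of the following injections". Next comes "A co-investigator will prepare the syringe to ensure blinding". The text does not say who flips the coin, whether anyone witnesses it, or where and when the result is written down. It mentions no list, envelopes or central system.

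On case mix, Section 1 (Background) says: "This study will examine intralesional corticosteroid injections for keloids, alopecia areata, and other indications while including a wider variety of injection sites". The same section says: "Keloid injections are often more painful than other injections".

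Section 10 (Statistical Plan) consists only of a sample-size statement. It plans for "independent control and experimental subjects with 1.1538 control(s) per experimental subject" and concludes that "we will need to study 34 experimental subjects and 39 control subjects". It describes no stratification and no covariate adjustment.

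**The concern.** There are two separate issues.

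**Verifiability.** With a sequence fixed in advance, anyone can later compare the allocations made with the allocations due. A coin leaves nothing to compare against. The staff present already know the patient's indication and site. If a flip were repeated or set aside, the protocol describes no record that would show it. At stake is the ability to demonstrate that the arms were formed by chance alone.

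**Balance.** The protocol names an influence on the outcome, keloid versus other indications, and enrols both kinds of patient in a trial of 73. It neither balances the factor at allocation nor uses it in the analysis. A chance difference in keloid share would move the pain comparison one way or the other, and the plan has no means of removing it.

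There is also a mismatch in the text: a 50% flip does not target the 39:34 ratio of Section 10.

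**Working it through.** **1. The plan's own figure.** Inputs from Section 10: difference 0.2, SD 0.3, type I error 0.05, power 0.8, ratio 1.1538. The normal approximation, two-sided, gives

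n(experimental) = (1 + 1/1.1538) × [0.3 × (1.960 + 0.842) / 0.2]² ≈ 33.0, and n(control) = 1.1538 × 33.0 ≈ 38.0.

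The two-sided noncentral t gives power 0.800 at 34 and 39. The stated 34 + 39 = 73 is reproduced.

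**2. Arm sizes under the coin.** The experimental arm size is Binomial(73, 0.5).

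- The 95% range is 28 to 45. Power is 0.780 at 28/45 and averages 0.797 over all splits.
- The smaller arm has 30 or fewer patients in 16.0% of trials.
- Exactly 34 experimental and 39 control occurs in 7.9% of trials. This says little, because even the most likely single split has a probability of only about 9%.
- An even 36/37 split gives power 0.802, so 1:1 needs no more than 73 patients.

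**3. Keloid balance under the coin.** Let m be the number of keloid patients. The documents do not give it; 10 to 36 is an assumption. With K ~ Binomial(m, 0.5) keloid and O ~ Binomial(73 − m, 0.5) other patients in one arm, the difference in keloid share is

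D = K/(K + O) − (m − K)/(73 − K − O).

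Its SD is close to 2 × √[p(1 − p)/73] with p = m/73. For m = 10 that is 2 × √(0.137 × 0.863/73) = 0.080. Summing over all values of K and O gives:

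| Keloid patients (assumed) | SD of D, points | At least 10 points | At least 15 points |
|---|---|---|---|
| 10 | 8.2 | 21.4% | 6.5% |
| 15 | 9.6 | 28.6% | 11.9% |
| 20 | 10.6 | 35.2% | 15.7% |
| 30 | 11.7 | 38.5% | 20.5% |
| 36 | 11.9 | 36.3% | 24.2% |

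Because counts are whole numbers, the 10-point column does not rise steadily. Over every m from 10 to 36 it runs from 21% to 41%, with the peak at m = 24.

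**4. What an imbalance does to the comparison.** The shift in the arm difference is D times the extra pain of a keloid injection, which the documents do not give.

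- If keloids add one within-group SD (assumption), a one-SD imbalance shifts the result by 0.08 to 0.12 SD. The planned difference is 0.2/0.3 = 0.67 SD, so this is 12% to 18% of it.
- The planned standard error is √(1/34 + 1/39) = 0.235 SD, or 0.235 × 0.3 = 0.070. If the SD of 0.3 already covers mixed indications, the shift is part of that standard error. The keloid effect δ must then satisfy p(1 − p)δ² ≤ 0.3². At p near one half δ is at most 0.6, and a one-SD imbalance shifts the result by at most 0.119 × 0.6 ≈ 0.07.
- If keloids add 2 points on the 0 to 10 scale (assumption), the shift is 2 × 0.08 to 2 × 0.12, or 0.16 to 0.24, against a target of 0.2. That cannot hold together with a total SD of 0.3.

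**5. After the change.** With blocks of 4 within each stratum (illustrative), keloid counts in the two arms differ by at most 2, and the keloid share by at most about 5 points for the counts examined.

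**The case against.** The strongest defence is that a fair coin is a legitimate randomization. It cannot be foreseen, and Section 6 places it after consent, so nobody can steer enrolment by knowing the next assignment. Simple randomization is unbiased and keeps the type I error valid whatever the keloid split. All of this stands. What it leaves open is a flip repeated or overridden after the result is seen, which unpredictability does not prevent.

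A reader might infer that the flips go unrecorded, or that a repeated flip could never be detected. The documents do not say so. They are silent on recording, and the arm must be noted somewhere for the trial to be analysed at all. They also give no sign that anyone would repeat a flip. The supportable statement is that no safeguard is described.

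A reader might also infer that keloid patients will be unevenly split, or that power suffers. The first is a probability that depends on an unstated keloid count; figures at 36 of 73 lie near the top of the range for the 15-point gap. The second is wrong: average power falls only from 80.0% to 79.7%. The 12% to 18% shift rests on an assumed keloid effect and may already sit inside the planned SD.

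Finally, indication is already collected, so adjustment alone would recover most of the precision. That is true, but no adjustment is planned. Blocks also bring some predictability that a coin lacks, and envelopes can be opened out of order. These are reasons to vary and hide block sizes and to log each opening, not reasons to keep the coin.

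**Conclusion.** The point holds as an inexpensive improvement that should be made before enrolment, because an allocation cannot be made checkable afterwards. The firmer part is verifiability: the protocol describes no sequence, concealment or log, so a repeated flip could go unnoticed. This rests on the text alone.

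The balance part is secondary. It rests on an assumed 10 to 36 keloid patients, and its effect on the pain comparison rests further on an assumed keloid effect. The harm is avoidable noise, not a false type I error rate or a material loss of power. The 50% flip in Section 5 and the 1.1538:1 ratio in Section 10 need reconciling in any case.

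**What to change.** - In Section 5, replace the coin flip with a computer-generated 1:1 list in permuted blocks of varying, undisclosed size, stratified by keloid versus other and generated before the first patient.
- Conceal the list in the study database or in sequentially numbered sealed opaque envelopes. State who generates it and who holds it.
- In Section 6, have the syringe preparer obtain the next assignment only after consent, indication and site are recorded, and log each assignment when it is made.
- In Section 10, include keloid versus other as a covariate in the comparison of pain scores, and restate the sample size as 1:1. With 36 and 37 patients power is about 80%, and the total remains 73.

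The cost is about an hour to generate the list and a short protocol amendment, with no extra patients or staff. The downside is slight predictability at block ends, which varying and hiding the block sizes limits.
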